4. STATISTICAL ANALYSES

This is an exploratory study for which no formal hypothesis testing will be done and thus no adjustment for multiplicity of testing will be performed.

All statistical analyses will be descriptive in nature. The statistics presented will be dependent on the variable type.

- Categorical variable number and percentage of participants; proportion, difference in proportions along with 95% CIs
- Continuous variable summary statistics including means, medians, ranges, and standard deviations. Absolute values and change from baseline TLGs as appropriate will be produced.

4.1 GENERAL CONSIDERATIONS

Disposition and protocol deviations listings and summaries will be based on all randomized participants. Analysis of safety will be based on the safety population. Pharmacodynamics and efficacy analysis will be based on the modified intention-to-treat (mITT) population. Pharmacokinetic analysis will be based on PK population. Immunogenicity analysis is based on the immunogenicity population.

For the treatment arms where additional patients have been recruited to proactively mitigate any impact of COVID-19 or force majeure events, the primary analysis will be performed when approximately 30 patients considered evaluable for the primary analysis reach the primary endpoint of Week 24 post EOT. If the primary analysis is positive for an experimental treatment arm, any additional patients that have been recruited to that treatment arm, will continue and be included in the final CSR.

Evaluable patients: A patient from the mITT population will be considered 'evaluable' if no more than two consecutive siRNA missing doses due to non-safety reasons (e.g., COVID-19 disruptions). This is based on the siRNA liver half-life of ~10 weeks.

estimated from ph1 data. Therefore, after two consecutive missing doses the drug left in the liver is expected to be \sim 40%, which was considered adequate as patients would restart dosing so up to 2 missing doses are not expected to have a major impact on the efficacy.

Evaluable patients in mITT population will be used to estimate the primary endpoint/estimand.

Any subject who does not have a virology parameter evaluation during the pre-specified window for 24-week Follow-up visit (either due to missing assessment or due to early withdrawal from the study or study treatment) will be considered as a non-responder. However, if the subject with missing evaluation is a responder both before and after the visit window, then the subject will be categorized as a responder for that visit.

Key definitions:

The following definitions will be used:

Baseline: The baseline value is defined as the last available valid (quantifiable continuous or categorical value), non-missing observation for each participant prior to first study drug administration. Repeat and unscheduled assessments will be included in the derivation of the baseline values.

HBsAq Loss: HBsAg loss refers to a negative/undetectable HBsAg level, HBsAg loss is defined HBsAg levels <0.05 IU/mL.

HBsAg Seroconversion: HBsAg seroconversion is defined as HBsAg loss (defined above) along with an anti-HBs result >= 10 IU/mL (positive)

For more granularity regarding HBsAg loss and seroconversion definitions, please refer to the table below.

Table 4 Definition HBsAg loss and seroconversion

HBsAg (quant)	HBsAg (qual)	HBsAg status	anti-HBs	Seroconversion status
Numerical				
value ≥ 0.05	Reactive	HBsAg present	<10 (Non-Reactive)	No
< 0.05	Reactive	HBsAg loss (present at low concentration) *	<10 (Non-Reactive)	No
< 0.05	Non- Reactive	HBsAg loss (confirmed)	<10 (Non-Reactive)	No
Numerical value ≥ 0.05	Non- Reactive	FLAG as discrepancy for review **	<10 (Non-Reactive)	No
Numerical value ≥ 0.05	Reactive	HBsAg present	≥ 10 (Reactive)	FLAG as double positive ***

< 0.05		HBsAg loss (present at low concentration) *	≥ 10 (Reactive)	Seroconversion *
< 0.05	Non- Reactive	HBsAg loss (confirmed)	≥ 10 (Reactive)	Seroconversion
Numerical value ≥ 0.05		FLAG as discrepancy for review **	≥ 10 (Reactive)	No

^{*} Follow longitudinal data for confirmation of HBsAg loss with the qualitative assay.

These values are based on the limits of detection, limits of quantification, and thresholds for positivity defined by the assay manufacturers and may be updated if any would change.

HBeAg Loss: HBeAg loss refers to a negative/non-reactive HBeAg level ((baseline HBeAg-positive participants).

HBeAq Seroconversion: HBeAg seroconversion is defined as an HBeAg loss (defined above) along with an anti-HBe result.

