Due to COVID-19 situation in March - May 2022, as of 31 May 2022 approximately 30-53% of participants in each treatment arm have missed study visits and siRNA drug administration at the site. As a result, a number of participants have consecutive visits missed with a potential impact on the evaluation of the primary endpoint due to incomplete data. To preserve the viability of the study, if the COVID-19 situation continues, or any future COVID-19 outbreaks or any force majeure (e.g. natural disasters, supply chain disruption, outbreak of hostilities etc.,) impacting participants, will lead to additional participants being recruited to the study to ensure that the number of participants per treatment arm with the full dose as per the randomized dose regimen remains approximately 30. The maximum number of additional participants to be recruited will be approximately 30 for each treatment arm.

The treatment period duration will be a maximum of 48 weeks, after which participants will enter a 48-week follow-up period. A shorter treatment duration (12 or 24 weeks) for NME combination arms, and a 48-week response-guided therapy (RGT) arm may be added following planned interim analyses; up to four interim analyses are planned for each treatment arm. Treatment arms that achieve 30% difference, compared to NUC control arm, for HBsAg loss at EOT or at follow-up weeks 12 and 24 (primary endpoint) may be expanded to accrue additional efficacy and safety data and to contribute to Phase 3 design planning as guided by the emerging data, for example, enrichment for

HBeAg positive or HBeAg negative participant populations. An expansion may also be triggered prior to EOT, for a treatment arm that gives an early indication of efficacy. The decision criteria to trigger an expansion arm in this case, will be documented as an appendix to the IMC/Scientific Oversight Committee (SOC) charter.

The total length of the study, from screening of the first participant to the end-of-study is expected to be approximately 3 to 5 years, depending on the number and timing of additional treatments arms that are added to the study.

The study duration for each participant will be approximately 2 years divided as follows:

- Screening period: up to 8 weeks.
- Treatment period: up to 48 weeks.
- Safety follow-up period: 48 weeks.

Table 2 Analysis Timing

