The timing of planned interim analyses and RGT below are illustrated based on a 48week treatment duration arm; for arms with shorter treatment duration, the number of the interim analyses as well as the RGT early treatment discontinuations will be adjusted accordingly.

Analysis	Timing of Analysis
First interim analysis	All participants in the study have completed their 12-week visit for a treatment arm or discontinued prematurely
Second interim analysis	All participants in the study have completed their 24-week visit for a treatment arm or discontinued prematurely
Third interim analysis	All participants in the study have completed their 48-week (EOT) visit for a treatment arm or discontinued prematurely
Fourth interim analysis	All participants in the study have completed their follow-up week 12 visit or discontinued prematurely
Primary	All participants in the study have completed their follow-up week 24 visit or discontinued prematurely
Final	The end-of-study for a treatment arm is defined as the date when the last participant completes their follow-up week 48 visit or discontinued prematurely

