2.1 STATISTICAL HYPOTHESES

As this is an exploratory study, no formal hypothesis testing will be performed.

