2.2 SAMPLE SIZE DETERMINATION

Approximately 30 participants will be randomized in each treatment arm. Approximately five replacement participants per arm may be replaced if participants have a dose regimen change or discontinue due to non-safety reasons. This is to ensure that the number of participants per arm of the randomized dose regimen remains close to 30.

In the event of COVID-19 or force majeure events that significantly impact compliance with the randomized dosing regimen, up to 30 additional participants may be enrolled per treatment arm to ensure that the randomized dose regimen remains close to 30. Criteria and the decision to enroll additional participants will be at the Sponsor's discretion.

The overall number of participants in this study will depend on the number of treatment arms that are included, which is not known at present.

The primary endpoint is the proportion of participants with HBsAg loss at 24 weeks post-EOT. Assuming a 3% NUC response rate, a sample size of 30 participants per arm provides 78% power to detect a pairwise 30% difference between a combination treatment arm and the NUC control arm. This is based on a two-treatment arm continuity corrected, two-sided, chi-squared test of equal proportions at a significance level of 5 %.

The sample size of combination treatment arms that achieve 30% delta for HBsAg loss at Week 48 (EOT) or follow-up Week 12 or 24 may be expanded up to approximately 100 participants. An expansion may also be triggered prior to EOT, for a treatment arm that gives an early indication of efficacy. The decision criteria to trigger an expansion arm in this case, will be documented as an appendix to the IMC/SOC charter. The expansion arm may be utilized to increase the precision of the efficacy treatment estimates; exploration of participant subgroups (e.g., baseline HBeAg status) and/or to gain additional safety data prior to Phase 3 clinical trials.

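### Entry of additional patients into the final report is tied to an undefined 'positive' primary result, and the non-positive case is not stated

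*SAP*

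**What the plan says.** SAP 4.1 deals with arms that recruited extra patients because of COVID-19 or force majeure. In those arms "the primary analysis will be performed when approximately 30 patients considered evaluable for the primary analysis reach the primary endpoint of Week 24 post EOT". It then says: "If the primary analysis is positive for an experimental treatment arm, any additional patients that have been recruited to that treatment arm, will continue". The sentence ends by saying that they "will continue and be included in the final CSR". Protocol 9.4.2 carries the same rule.

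Three things are left open.

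- **What 'positive' means.** SAP 2.1 says: "As this is an exploratory study, no formal hypothesis testing will be performed". The only numerical benchmark in either document is the 30-point difference used for expansion and for opening new arms, and nothing links it to this sentence.
- **What happens if the result is not positive.**
- **What happens to additional control patients.** The sentence speaks of experimental arms only.

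Other parts of the plan carry no such condition. Protocol section 9 holds each arm's complete-data analysis until every participant in the arm has finished follow-up or left early. The safety and mITT definitions (protocol 9.3, SAP section 3) depend on randomisation and dosing, not on a result. SAP 4.2.3 plans a sensitivity analysis on the whole mITT population. SAP Table 2 (section 1.2) times the primary analysis differently again: "All participants in the study have completed their follow-up week 24 visit or discontinued prematurely".

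**The concern.** If the sentence is applied as a rule, an arm whose first 30 or so evaluable patients do well is updated with more data, and an arm whose first 30 do badly is not. What the final report contains then depends on what the primary analysis showed. The study is open-label, interim results are reviewed by an internal committee and the sponsor retains all decision-making authority, so an undefined trigger would be interpreted after the data are known.

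At stake are the later efficacy and safety data of randomised participants in arms that look negative, and a common basis for reporting the arms of one platform that is meant to inform Phase 3 planning. A programmer also cannot follow both this sentence, read as a condition, and the unconditional passages for a non-positive arm.

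**Working it through.** **1. The plan's own figure.** SAP 2.2: "Assuming a 3% NUC response rate, a sample size of 30 participants per arm provides 78% power" for a 30-point difference, using a two-sided, continuity-corrected chi-squared test at 5%. With n = 30, rates 0.33 and 0.03, and mean rate 0.18:

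- Continuity-adjusted size: n' = n(1 - 1/(nΔ))² = 30(1 - 1/9)² = 23.70.
- z = [√23.70 × 0.30 - 1.96√(2 × 0.18 × 0.82)] / √(0.33 × 0.67 + 0.03 × 0.97) = (1.461 - 1.065)/0.500 = 0.791.
- Power = 78.6%, which agrees with the stated 78%. The rule examined here does not change it, because the roughly 30 evaluable patients are fixed before the result is known.

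**2. How many patients could be affected.** SAP 2.2 allows that "up to 30 additional participants may be enrolled per treatment arm". SAP 1.2 reports that "approximately 30-53% of participants in each treatment arm have missed study visits". The plan does not say how many of these are unevaluable. Assume all of them are, that the full 30 are added, and that all 30 added are evaluable:

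- 30% affected: 9 replacements are needed, surplus 30 - 9 = 21.
- 53% affected: 15.9 replacements are needed, surplus 30 - 15.9 = 14.1.

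The replacements enter the primary analysis whatever its result. Only the surplus, m, can depend on it. The full possible range is 0 to 30; I use 14, 21 and 30.

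**3. Effect on the final estimate.** All outcomes of 30 versus 30 patients were enumerated with exact binomial probabilities. The control rate is 3% and the experimental rate 23%, a true difference of 20 points. The m surplus patients are added to the experimental arm only if the first 30 are positive. Since 'positive' is undefined, two rules were assumed: (a) the continuity-corrected, unstratified 95% interval excludes zero in favour of the combination; (b) the observed difference is at least 30 points.

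The surplus patients average the true rate, so

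shift = -P(positive) × (mean experimental rate in positive arms - true rate) × m/(30 + m).

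| Rule | P(positive) | Mean experimental rate if positive | m = 14 | m = 21 | m = 30 |
|---|---|---|---|---|---|
| (a) interval excludes zero | 0.5405 | 27.92% | -0.8 | -1.1 | -1.3 |
| (b) 30-point rule | 0.1562 | 34.67% | -0.6 | -0.7 | -0.9 |

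For (a) with m = 30: 0.5405 × 4.92 × 0.5 = 1.3 points. For (b) with m = 30: 0.1562 × 11.67 × 0.5 = 0.9 points. Reporting the surplus unconditionally gives a shift of zero.

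**4. Positive and non-positive arms separately (m = 30).**

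- Rule (a): positive arms move from 26.0 to 23.6 points. Non-positive arms report 12.9, against 15.8 had the surplus been counted. The average over all arms is 18.7.
- Rule (b): positive arms move from 33.1 to 27.2. Non-positive arms report 17.6, against 18.7. The average over all arms is 19.1.

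**5. At the design difference of 30 points.** Under rule (b) 57% of arms are positive, so the surplus would go unreported in 43%. With m = 30 those arms report 21.7 points, against 25.3 with the surplus counted, and the overall shift is -1.6 points. At zero true difference the shift is about 0.

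**6. Scale.** The 95% half-width for 23% versus 3% at 30 per arm is 1.96√(0.23 × 0.77/30 + 0.03 × 0.97/30) = 16 points. With 60 in the experimental arm it is 1.96√(0.23 × 0.77/60 + 0.03 × 0.97/30) = 12 points.

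**The case against.** The strongest reply is that the sentence states one branch only. It says what follows a positive result; it does not say that additional patients are left out otherwise. Protocol section 9, the safety and mITT definitions and the whole-mITT sensitivity analysis all point to unconditional inclusion, and for safety they say so plainly. The study is exploratory, the primary set is fixed before the result, and the protocol says that the study is not powered to compare experimental arms with each other. This stands in part: the defect is a missing branch that conflicts with other rules, not a declared exclusion. It does not dispose of the point, because the specific sentence makes the result the stated condition and nothing says which text prevails.

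Three stronger inferences are tempting and not supported.

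- **That the rule inflates positive findings.** It does the opposite: added data pull positive arms back towards the truth, and the net shift is against the treatment.
- **That it causes the low figure in non-positive arms (12.9 points against a true 20).** That figure is the primary result among arms selected for being low. Even with the surplus counted it would be 15.8.
- **That 30 patients per arm are at risk.** Thirty is a ceiling. It would require all 30 original patients to be evaluable, in which case no top-up was needed.

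It is also fair to say that whether participants stay on study in a non-positive arm is a conduct decision for the sponsor, separate from whether data already collected are reported.

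**Conclusion.** The point holds in limited form. The plan ties continuation and entry to the final CSR to an undefined 'positive' result and leaves the non-positive case unstated, so on the natural reading the final data for surplus patients depend on the result. The primary analysis and its stated power are not affected.

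At a true 20-point difference the numerical shift in the final estimate is small: about -0.8 to -1.3 points under the interval rule and -0.6 to -0.9 under the 30-point rule, against a half-width of about 16. The main cost is follow-up data from randomised participants going unreported, and a less precise estimate, in arms that look negative.

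These figures rest on assumptions that the documents do not supply: the two meanings given to 'positive', a surplus of 14 to 30, no stratification, and additional patients in the experimental arm only.

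**What to change.** In protocol 9.4.2 and SAP 4.1, replace the condition on inclusion with a statement that all data collected on every additional randomised participant, in experimental and control arms and whatever the primary result, are included in the final CSR: in the efficacy analyses (mITT and evaluable) and in the safety analyses. Show the estimates at the primary cut and at the final cut side by side.

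Reconcile the sentence with protocol section 9, SAP section 3 and SAP Table 2, including which trigger times the primary analysis in arms with additional patients. If 'positive' is kept for any decision on whether participants continue, define it before the primary data are seen. What that decision should be is for the sponsor and is not proposed here.

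The cost is a sentence in each document, the matching adjustment to SAP Table 2, and one extra column in the efficacy output. No new patients are needed.

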9.4 STATISTICAL ANALYSES

9.4.1 Demographics and Baseline Characteristics

Descriptive statistics will be generated for demographic and baseline disease characteristics including sex, race, ethnicity, origin (for Asian participants only), age, weight, height, body mass index, HBV DNA and HBsAg levels, and HBV history including but not limited to duration of HBV disease, likely route of transmission, HBV genotype, HBeAg status, previous HBV treatments, and length of time on NUCs.

9.4.2 Efficacy Analyses

All efficacy analyses will be based on the efficacy analysis population.

For the treatment arms where additional patients have been recruited to proactively mitigate any impact of COVID-19 or force majeure events, the primary analysis will be performed when approximately 30 patients considered evaluable for the primary analysis reach the primary endpoint of Week 24 post EOT. The criteria to assess evaluability will be described in the SAP. If the primary analysis is positive for an experimental treatment arm, any additional patients that have been recruited to that treatment arm, will continue and be included in the final CSR.

Any sensitivity analyses including patients considered 'unevaluable' for the primary analysis will be specified in the SAP.

For the primary endpoint (% participants with HBsAg loss at 24 weeks post-EOT), the estimated treatment difference adjusted for baseline HBsAg level, along with the associated 95% Confidence Interval in the proportion of participants with HBsAg loss at 24 weeks post-EOT between the experimental and the associated control arm will be provided.

Confidence Intervals will be estimated using Cochran-Mantel-Haenszel (CMH) weighting method with continuity correction (Lu 2008). Participants with missing or no response assessments will be classified as non-responders.

Summary statistics will be produced by treatment arm for each of the endpoints defined Table 4. In addition, graphical displays will be produced of mean and individual participant data as appropriate.

 Table 4
 Efficacy Statistical Analysis Methods

Endpoint	Statistical Analysis Methods
Primary	Treatment effect with associated binomial CI
Secondary	Descriptive statistics

9.4.3 Safety Analyses

All safety analyses will be based on the safety analysis population grouped according to the treatment assigned at randomization.

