3. ANALYSIS SETS

The participant analysis sets for the purposes of analyses are defined in Table 3.

Table 3 Participant Analysis Sets

Population	Description
Safety	All participants randomized to a treatment regimen who received at least one dose of any drug for their assigned treatment regimen, whether prematurely withdrawn from the study or not, will be included in the safety analysis.
Modified ITT	All participants who were randomized and received at least one dose of each drug for their assigned treatment regimen. Participants will be analyzed according to the treatment arm to which they were randomized.

Pharmacokinetic	Participants will be excluded from the PK analysis population if they significantly violate the inclusion or exclusion criteria, deviate significantly from the protocol, or if data are unavailable or incomplete which may influence the PK analysis. Excluded cases will be documented together with the reason for exclusion. All decisions on exclusions from the analysis will be made prior to database closure.
Immunogenicity	All Participants who had at least one pre- dose (baseline) or at least one post-dose ADA assessment will be included and analyzed according to the treatment they actually received or were allocated to receive,

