4.2 PRIMARY ENDPOINTS/ESTIMANDS ANALYSES

4.2.1 Definition of Primary Endpoint(s)/Estimand(s)

Definition of Primary Endpoint:

The primary endpoint is HBsAg loss (qHBsAg <0.05 IU/mL) at week 24 post EOT.

The primary endpoint is calculated for each treatment arm as:

% participants with HBsAg loss= (Number of participants with HBsAg loss / total number of participants) *100

The percentage of participants with HBsAg loss will analyzed using evaluable patients from the mITT population.

Definition of Primary Estimand:

In line with the Estimands addendum to ICH E9, the primary efficacy estimand is defined as follows-

The difference between proportions of HBsAg loss (qHBsAg <0.05 IU/mL) at week 24 follow-up in virologically suppressed adult CHB participants on established NUC therapy, with preserved liver function and without significant fibrosis/cirrhosis, treated with

^{**} Evaluate numerical and longitudinal data to understand the discrepancy.

^{***} Depending on numerical values, these may be rare cases of double positive (HBsAg and anti-HBs) usually seen from baseline. Seroconversion will need to be interpreted using longitudinal data.

combination therapy* versus NUC, irrespective of adherence to IMP or whether prohibited medication and/or food has been taken.

*treatment and dose levels will vary depending on the combination arm and are specified in the relevant arm specific appendix.

The primary efficacy estimand is described by the following five attributes:

- a) **Population**: Evaluable patients from the mITT population as defined in section 3. These will be CHB adult participants who are virologically suppressed for more than 6 months on established NUC therapy as defined by the inclusion and exclusion criteria listed in Protocol WV41073 section 5.
- **b) Primary Endpoint**: % participants with HBsAg loss (qHBsAg <0.05 IU/ml) at 24 weeks post-EOT.
- c) Population level summary: The difference between proportions of HBsAg loss (qHBsAg <0.05 IU/mL) between NME combination over the control arm at week 24 post-EOT
- **d)** Treatment conditions: Treatment and dose levels will vary depending on combination arms and are specified in the relevant arm specific appendix.
- e) Intercurrent Event (ICE):

Table 5 Intercurrent Events Impacting Primary Analyses:

Intercurrent Events	SDR/ NSDR	Estimand Approach
Participants with dose interruptions or switching dose/frequency	SDR	Treatment Policy

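### The primary analysis removes siRNA-arm patients with long non-safety dosing gaps, which contradicts the treatment-policy estimand and leaves the trigger of COVID-19 scenario 1 selecting nobody

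*SAP*

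**What the plan says.** **Analysis set.** SAP section 3 defines modified ITT as "All participants who were randomized and received at least one dose of each drug for their assigned treatment regimen", with no condition on later dosing. SAP 4.1 then adds the evaluability rule: "A patient from the mITT population will be considered 'evaluable' if no more than two consecutive siRNA missing doses due to non-safety reasons". The reason given is a liver half-life of about 10 weeks, leaving roughly 40% of the drug after two missed doses, "as patients would restart dosing so up to 2 missing doses are not expected to have a major impact on the efficacy". The rule governs the estimate itself: "Evaluable patients in mITT population will be used to estimate the primary endpoint/estimand". SAP 4.2.2 repeats this for the main analysis.

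**Estimand.** In SAP 4.2.1 the population attribute is "Evaluable patients from the mITT population as defined in section 3". The narrative definition compares the arms whether or not patients adhered to study drug. Table 5 lists COVID-19 missed doses that could seriously affect efficacy, and assigns them to treatment policy. The text below the table says that observed values are used whatever the intercurrent event.

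**Sensitivity and supplementary analyses.** SAP 4.2.3 plans a completer analysis and a full-mITT analysis that includes unevaluable patients. SAP 4.2.4 plans a hypothetical-strategy analysis for COVID-19 or other non-safety gaps in two scenarios: runs of at least three, and of at least two, missed siRNA doses. It states that the population is that of the primary estimand.

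**Protocol.** Protocol 9.4.2 foresees an evaluable primary set, leaves the criteria to the SAP, and adds: "Any sensitivity analyses including patients considered 'unevaluable' for the primary analysis will be specified in the SAP".

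**The concern.** The rule is applied after randomisation and can remove patients only from arms that contain siRNA. A NUC control with the same lockdown disruption stays in and, if follow-up Week 24 is missing, normally counts as a non-responder.

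Two consequences follow from the text. First, one part of the estimand removes patients with long non-safety siRNA gaps, while two other parts say that their observed values are used. A reader of the report could not tell which treatment effect the headline estimates. Second, the supplementary analysis is meant to show what would have happened without the long gaps, but it runs in a population from which those gaps have already been removed.

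**Working it through.** **1. The plan's own figures.** The residual-drug figure behind the cut is 2^(−gap/10), with the gap in weeks and siRNA given every 4 weeks.

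- Two missed doses, 12 weeks between doses: 2^(−1.2) = 43.5%, consistent with the SAP's approximate 40%.
- Three missed doses, 16 weeks: 2^(−1.6) = 33.0%.

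On the SAP's own half-life, the cut therefore separates patients whose residual exposure differs only modestly.

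The stated power (78% for 33% against 3%, 30 per arm, continuity-corrected) also reproduces. Effective n = 30 × (1 − 1/(30 × 0.30))² = 23.7, which gives 78.6%. It is not in dispute.

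**2. Who can fail the rule.** SAP Appendix 1 gives controls background NUC only. They have no scheduled siRNA doses, so none can be unevaluable.

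**3. Estimand parts side by side, for non-safety siRNA gaps.**

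| Longest run of missed doses | Population attribute (4.2.1 with 4.1) | Narrative and Table 5 |
|---|---|---|
| 0 to 2 | kept | kept |
| 3 or more | removed | kept, observed values used |

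SAP 4.1 expects no major effect from up to two misses. For siRNA, the Table 5 event of missed doses that could seriously affect efficacy therefore mainly describes the second row, which is the row the population attribute removes. Gaps for safety reasons, gaps of up to two doses, and missed doses of other drugs are unaffected.

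**4. Supplementary scenarios.** Evaluable means a longest non-safety run of at most 2.

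- Scenario 1 needs a run of at least 3. The overlap with the evaluable set is empty, so no data are set to missing by this trigger.
- Scenario 2 needs a run of at least 2. The overlap is runs of exactly 2.

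**5. Possible size (illustration; the counts and response rates are assumed).** If k patients with response rate pU are excluded from an arm with 30 evaluable patients at rate pE, the evaluable rate exceeds the full rate by k/(30 + k) × (pE − pU). Take pE = 10/30 and control 1/30, so the evaluable difference is 33.3 − 3.3 = 30.0 points.

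| Response in excluded patients | Full difference, k = 5 | Full difference, k = 9 |
|---|---|---|
| none | 10/35 − 1/30 = 25.2 | 10/39 − 1/30 = 22.3 |
| half the evaluable rate | 27.6 | 26.2 |
| equal | 30.0 | 30.0 |
| 1.5 times | 32.4 | 33.8 |

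Unstratified Miettinen-Nurminen 95% intervals, shown for scale only because the SAP uses CMH weights with continuity correction, are 11.8 to 48.7 for 10/30, 8.2 to 42.6 for 10/35 and 5.9 to 38.6 for 10/39.

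The 30–53% in SAP 1.2 is not used. It counts participants with missed visits and siRNA dosing by 31 May 2022, not runs of three or more doses.

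**The case against.** **Scenario 1 is not empty.** A reader might infer that it has nothing to impute and must return the primary result. The documents do not support that. SAP Appendix 6 also imputes values missing because of COVID-19, which can occur in evaluable patients and in controls who count as non-responders in the primary analysis. The two results may differ. In addition, the data-flag sentence in 4.2.4 omits the word consecutive, so scattered misses might be flagged, and a run mixing safety and non-safety misses is not clearly assigned. What stands is narrower: the scenario's defined dose-gap trigger, read with the non-safety reason, selects nobody in the population named.

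**The SAP departs from the protocol.** A reader might infer this because the paragraph in Protocol 9.4.2 opens "For the treatment arms where additional patients have been recruited to proactively mitigate any impact of COVID-19 or force majeure events". That clause governs when the analysis is done. The criteria are left to the SAP, and the sentence on unevaluable patients carries no restriction by arm. A departure is not clearly shown.

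**Permanent stops.** It is tempting to say that the SAP treats these as failures. Table 5 keeps their observed values. SAP 4.1 imposes non-response only where the Week 24 evaluation is missing, including "due to early withdrawal from the study or study treatment) will be considered as a non-responder". Whether a permanent non-safety stop counts as a run of missed doses is simply not stated.

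**Controls may be selected too.** SAP Appendix 1 refers to controls who completed the study for each reporting event. That is a different criterion and does not make the siRNA rule two-sided.

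**Low stakes.** The study is exploratory with no formal testing, and full mITT is already planned as a sensitivity analysis. Both are true and limit the weight of the point. Neither makes the estimand consistent, and neither gives scenario 1 the patients it was written for.

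**Conclusion.** The point holds on the text alone, without any numerical assumption. For non-safety siRNA gaps of three or more consecutive doses, the population attribute contradicts the narrative and Table 5. SAP 4.2.4 names a population in which scenario 1's trigger cannot fire and scenario 2 reaches only gaps of exactly two. This should be corrected before the primary readout.

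The size and direction of any bias cannot be derived from the documents. Under the assumed counts above, the evaluable-only difference could be 7.7 points too high (30.0 − 22.3) or 3.8 points too low (33.8 − 30.0), and it is unchanged if excluded patients respond equally. Zero response is an extreme, given the modest difference in residual exposure across the cut.

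A reader might infer that the rule inflates efficacy or could trigger an arm expansion. The documents support neither: SAP 2.2 makes expansion optional and names no analysis set for it.

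**What to change.** 1. In SAP 4.2.4, name full mITT, including unevaluable patients, as the population, so that both scenarios can run as described. The data-flag sentence should also say whether the misses must be consecutive.
2. In SAP 4.2.1, reconcile the population attribute with the narrative and Table 5. If the evaluable set stays primary, withdraw the treatment-policy and adherence-independent claim for the excluded gaps, and report the full-mITT estimate beside the headline.

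Making full mITT primary is an option for the sponsor, not a required change. It would need Protocol 9.4.2 to be aligned, and it trades against the protocol's aim of about 30 patients per arm on the full randomised regimen.

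The cost of the two required changes is SAP wording and the display of one already planned analysis next to the headline, where the result may look less favourable. No extra patients are needed.
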